**Table 11: Immune-Related Response Criteria Definitions**

Index Lesion Definition	Non-Index Lesion Definition	New Measurable Lesions	New Unmeasurable Lesions	Percent change in tumor burden (including new lesions when present)	Overall irRC Response
Complete Response	Complete Response	No	No	-100%	irCR
Partial Response	Any	Any	Any	≥ -50% <-50% <+25%	irPR to irSD

Index Lesion Definition	Non-Index Lesion Definition	New Measurable Lesions	New Unmeasurable Lesions	Percent change in tumor burden (including measurable new lesions when present)	Overall irRC Response
Stable Disease	Any	Any	Any	>+25% <-50% <+25%	irPD to irSD
Progressive Disease	Any	Any	Any	>+25% ≥+25%	irPD irPD

***Immune-Related Best Overall Response Using irRC (irBOR)***

irBOR is the best confirmed irRC overall response over the study as a whole, recorded between the date of first dose until the last tumor assessment before subsequent therapy (except for local palliative radiotherapy for painful bone lesions) for the individual subject in the study. For the assessment of irBOR, all available assessments per subject are considered.

irCR or irPR determinations included in the irBOR assessment must be confirmed by a second (confirmatory) evaluation meeting the criteria for response and performed no less than 4 weeks after the criteria for response are first met.

**Response Endpoints**

Ipilimumab is expected to trigger immune-mediated responses, which require activation of the immune system prior to the observation of clinical responses. Such immune activation may take weeks to months to be evident. Some patients may have objective volume increase of tumor lesions or other disease parameters (based on study indication, ie, hematologic malignancies) within 12 weeks following the start of ipilimumab dosing. Such patients may not have had sufficient time to develop the required immune activation or, in some patients, tumor volume or other disease parameter increases may represent infiltration of lymphocytes into the original tumor or blood. In conventional studies, such tumor volume or relevant laboratory parameter increases during the first 12 weeks of the study would constitute PD and lead to discontinuation of imaging to detect response, thus disregarding the potential for subsequent immune-mediated clinical response.

Therefore, patients with tumor volume increase detected or lack of laboratory parameter response documentation prior to week 12 but without rapid clinical deterioration should continue to be treated with ipilimumab and clinically observed with a stringent imaging schedule to allow detection of a subsequent tumor response. This will improve the overall assessment of the clinical activity of ipilimumab and more likely

capture its true potential to induce clinical responses. Tumor assessments will be made using modified WHO criteria.

## 7.0 STATISTICAL PLAN

### 7.1 Sample Size Determination

Overall, this study will require 32 evaluable patients. We estimate that we will accrue 1-2 patients per month; therefore, thus, the minimum study duration will be 16 months (2 accruals per month) and the maximum is 32 months (1 accrual per month for 32 patients).

Current literature and experience with ipilimumab in metastatic melanoma in this patient population shows that we can expect ipilimumab + SABR will not be considered promising in this patient population if at most 15% of patients are progression-free and alive at 6 months, because that is the expected 6 month PFS for ipilimumab alone. For this agent to be considered promising in this patient population, we would expect an improvement in the 6-month PFS rate to at least 35% with this regimen in this patient population. Constraining the Type I and II error rates to 10% each, the study design will require 32 evaluable patients to test these hypotheses regarding the 6-month PFS rate with ipilimumab when given in combination with the stereotactic ablative radiation therapy in this patient population. If we see at least 8 patients who have are alive and progression-free at 6 months after initiation of treatment out of the 32 evaluable patients, we will consider this sufficient evidence that this regimen has promising activity in this patient population. Otherwise, if 7 or fewer patients have are alive and progression-free at 6 months, we will consider this regimen to not be sufficiently active in this population of oligometastatic melanoma patients.

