
Study Product, Dose, Route, Regimen
	
Ipilimumab will be administered on week 1 at a dose of 3 mg/kg. Subsequent cycles of ipilimumab will be given every three weeks (week 4, 7, & 10).
 
SABR will be delivered between the second and third doses of ipilimumab(week 5-6) using the following suggested schedules: 18 Gy x 3 to lung, 10 Gy x 5 to liver, 6 Gy x 6 to nodal stations, 12 Gy x 3 to adrenal, 18 Gy x 1 to bone, and 24 Gy x 1, 18 Gy x 1, 15 Gy x 1 to < 2.0 cm, 2.0-3.0 cm, and >3 cm brain metastases, respectively.
 
Duration of therapy: Patients will receive at least 12 weeks of therapy and will be observed for toxicity for 90 days after the last ipilimumab infusion. Patients will remain on study until evidence of progression or death.

Duration of administration
	
12 weeks

Reference therapy
	
NA

Statistical Methodology	
Overall, this study will require 32 evaluable patients. We estimate that we will accrue 1-2 patients per month. Thus, the minimum study duration will be 16 months and the maximum is 32 months.
 
Current literature and experience with maintenance therapy in this patient population shows that we can expect that this treatment regimen will not be considered promising in this patient population if at most 15% of patients are progression-free and alive at 6 months. For this agent to be considered promising in this patient population, we would expect an improvement in the 6-month PFS rate to at least 35% with this regimen in this patient population. Constraining the Type I and II error rates to 10% each, a 2-stage phase II Simon minimax study design will require 32 evaluable patients to test these hypotheses regarding the 6-month PFS rate with ipilimumab when given in combination with the stereotactic ablative radiation therapy in this patient population.

----------------------------	---

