The safety and efficacy of Ipilimumab were investigated in a randomized (3:1:1), double-blind, double-dummy study that included 676 randomized patients with unresectable or metastatic melanoma previously treated with one or more of the following: aldesleukin, dacarbazine, temozolomide, fotemustine, or carboplatin . Of these 676 patients, 403 were randomized to receive Ipilimumab at 3 mg/kg in combination with an investigational peptide vaccine with incomplete Freund's adjuvant (gp100), 137 were randomized to receive Ipilimumab at 3 mg/kg, and 136 were randomized to receive gp100 alone. The study enrolled only patients with HLA-A2\*0201 genotype; this HLA genotype facilitates the immune presentation of the investigational peptide vaccine. The study excluded patients with active autoimmune disease or those receiving systemic immunosuppression for organ transplantation. Ipilimumab /placebo was administered at 3 mg/kg as an intravenous infusion every 3 weeks for four doses. Gp100/placebo was administered at a dose of 2 mg peptide by deep subcutaneous injection every 3 weeks for four doses. Assessment of tumor response was conducted at weeks 12 and 24, and every 3 months thereafter. Patients with evidence of objective tumor response at 12 or 24 weeks had assessment for confirmation of durability of response at 16 or 28 weeks, respectively.

The major efficacy outcome measure was overall survival (OS) in the Ipilimumab + gp100 arm compared to that in the gp100 arm. Secondary efficacy outcome measures were OS in the Ipilimumab + gp100 arm compared to the Ipilimumab arm, OS in the

Ipilimumab arm compared to the gp100 arm, best overall response rate (BORR) at week 24 between each of the study arms, and duration of response. Of the randomized patients, 61%, 59%, and 54% in the Ipilimumab +gp100, Ipilimumab, and gp100 arms, respectively, were men. Twenty-nine percent were  $\geq 65$  years of age, the median age was 57 years, 71% had M1c stage, 12% had a history of previously treated brain metastasis, 98% had ECOG performance status of 0 and 1, 23% had received aldesleukin and 38% had elevated LDH level. Sixty-one percent of patients randomized to either Ipilimumab-containing arm received all 4 planned doses. The median duration of follow-up was 8.9 months.

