### 1.2.3 The role of SABR in melanoma:

SABR is an advanced radiation therapy technique which delivers a high dose of photon-based radiation therapy to a tumor target with a high degree of conformality, thus minimizing the dose to nearby healthy tissues. SABR uses image-guided radiation therapy techniques like daily pretreatment kilovoltage or megavoltage CT scans and various forms of motion management to deliver high doses of radiation therapy to a tumor target in 1-5 total ablative treatments. SABR has become an exciting byproduct of recent advances in linear accelerator design and improvements in the physics of motion management. Most large cancer centers now have a robust experience treating brain, lung, liver, and skeletal metastases with SABR. Indeed, the local control rates from SABR to metastases in the lung has been so exciting that several of national clinical trials are

now enrolling or in development to compare the efficacy of SABR to that of invasive surgical resection (RTOG 1021).

SABR was first applied to melanoma metastases to the vertebral bodies and brain with encouraging outcomes. Aggressive targeting of individual melanoma sites of metastasis via SABR to the lungs and liver has been reported by Stinauer who treated 28 metastatic lesions in 17 patients using a SABR regimen of 40-50 Gy in 5 total fractions or 42-60 Gy in 3 total fractions. The local control of metastases treated was 88% at 18 months and the median overall survival was 22.2 months.

The importance of aggressive local disease control and its ability to improve survival in melanoma was recently highlighted by the SWOG 9430 trial. This phase II trial in 77 patients with oligometastatic melanoma examined the value of an attempted complete surgical resection of all sites of disease. They found a median overall survival of 21 months compared with 6.2 months in patients involved in cooperative group systemic therapy alone trials. Likewise, they found a median relapse-free survival of 5 months compared with the historical baseline of 1.7 months on cooperative group systemic agent alone trials. This trial suggests that aggressive treatment of oligometastatic disease may prolong survival. The potential advantages of using SABR as the local control method are that SABR is non-invasive and requires minimal recovery time.

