**Figure 3: CA184024 Kaplan-Meier Plot of Overall Survival - All Randomized Subjects**

One, two and three year survival rates were 47.3%, 28.5% and 20.8% in the ipilimumab arm, and 36.3%, 17.9% and 12.2% in the placebo arm.

PFS, a secondary end-point, was also prolonged by the addition ipilimumab, HR 0.76 (95% CI, 0.63 - 0.93). The median PFS was 2.8 months in the ipilimumab and vs 2.6 months in the placebo arm,  $p = 0.006$ .

BORR was increased from 10.3% in the placebo arm to 15.2% in the ipilimumab arm (Table 7). More importantly, duration of response was more than twice as long in the ipilimumab arm (19.3 months) than in the placebo arm (8.1 months).

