## 3.0 STUDY DESIGN

### 3.1 General Design

Phase II, single-arm, open label, non-randomized study with ipilimumab and SABR as outlined in the treatment plan. Patients with oligometastatic melanoma who are treatment naïve or previously treated with a non-ipilimumab regimen will be treated with ipilimumab 3 mg/kg. Each ipilimumab cycle is 3 weeks (21 days) with treatment administered on day 1. SABR to 1-3 metastatic sites will be delivered in-between the second and third ipilimumab doses. All patients are expected to complete four cycles of ipilimumab. Response will be assessed with contrasted CT imaging prior to ipilimumab therapy and after the 4th ipilimumab treatment using mWHO & irRC criteria. Correlative studies will focus on identifying changes in blood and serum T-cell activation and expression markers when SABR is added to the ipilimumab regimen and to evaluate the effect of key melanoma genomic DNA mutations on outcomes like response, progression-free survival and overall survival with this regimen.

The study will consist of the following schedule:

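### The 15% null is presented as the ipilimumab-alone rate for this trial's patients, but its cited source is a differently selected population, so the 10% type I error is not established for them

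*Combined protocol and SAP*

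**What the plan says.** Section 7.1 sets the null 6-month PFS rate at 15%. The regimen is not promising "if at most 15% of patients are progression-free and alive at 6 months, because that is the expected 6 month PFS for ipilimumab alone", with a citation to reference 1. The sentence opens "Current literature and experience with ipilimumab in metastatic melanoma in this patient population shows", so the rate is offered as one that holds for the patients in this trial. The target is 35%, type I and type II error are limited to 10% each, and 8 or more of 32 evaluable patients progression-free and alive at 6 months counts as promising activity in oligometastatic melanoma.

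The Study Summary uses the same 15% but rests it on something else: "Current literature and experience with maintenance therapy in this patient population". No maintenance-therapy data supporting a 15% rate are presented.

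On who is studied:

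- Section 1.2.1 describes reference 1 as a randomised trial in patients who had all received prior systemic treatment. It mentions no limit on the number of metastatic sites.
- Section 3.1 of this protocol admits both treatment-naive and previously treated patients with oligometastatic disease, and "SABR to 1-3 metastatic sites will be delivered in-between the second and third ipilimumab doses". Section 4.1 requires 1-3 sites that SABR can target.
- Section 7.3 restricts the primary analysis to patients who received at least two ipilimumab doses and SABR.

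**The concern.** This is a single-arm trial, so the historical rate is the only comparator for the primary decision. If patients chosen for few, treatable sites would do better than 15% on ipilimumab alone, the rule can be met without any contribution from SABR.

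Three features separate these patients from the cited source: number of sites, admission of treatment-naive patients, and the requirement to have reached SABR. The last matters because sections 3.2 and 7.2 count from enrolment while SABR comes around weeks 5-6. Patients who fail before SABR leave the denominator. No section adjusts the 15% for these differences, reports the 6-month PFS observed in the source, or gives a sensitivity range.

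At stake is the meaning of a positive result. Section 7.1 would call 8/32 promising activity in this population, and section 13.1 frames the question as whether adding SABR to ipilimumab improves PFS.

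**Working it through.** **Inputs.** From section 7.1: n = 32, cut-off 8, null 15%, target 35%, both errors at most 10%. The ipilimumab-alone rate in patients with 1-3 SABR-targetable sites who reach SABR is not in the documents. It is treated below as an assumption over 15-30%.

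**Formula.** With X binomial (32, p), P(X ≥ 8) = 1 − Σ C(32, x) pˣ (1 − p)³²⁻ˣ, summed over x = 0 to 7.

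**Step 1: reproduce the plan.**

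- p = 0.15: P(X ≤ 7) = 0.9042, so the type I error is 1 − 0.9042 = 0.0958.
- p = 0.35: P(X ≥ 8) = 0.9182, the power.
- A search over n gives 32 with cut-off 8 as the smallest single-stage design meeting both limits. A Simon two-stage minimax design with the same inputs also gives 32 with success at 8 or more (type I error 0.0906, power 0.9053).

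The arithmetic of the design is right. The open question is the 15% input.

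**Step 2: find the slack.** P(X ≥ 8) is 0.0958 at p = 0.150 and 0.1018 at p = 0.152; it reaches 0.10 at about p = 0.151. The stated error limit therefore tolerates almost no upward error in the reference rate.

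**Step 3: error over the assumed range, with no SABR benefit.**

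| Assumed ipilimumab-alone 6-month PFS | P(8 or more of 32) |
|---|---|
| 15% | 9.6% |
| 18% | 20.6% |
| 20% | 30.2% |
| 25% | 56.8% |
| 30% | 78.8% |

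**Step 4: what holding the error would cost.** With n = 32 and type I error at most 10%, the cut-off would be:

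- 10 at a 20% null (power 73% at 35%);
- 12 at a 25% null (power 45%);
- 14 at a 30% null (power 20%).

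With the target kept at 35%, 90% power would need 61 patients at a 20% null or 143 at a 25% null, single stage. Redesign is therefore expensive relative to stating the limitation.

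**The case against.** A historical null is a normal choice in a single-arm phase II, and section 7.1 claims activity for the regimen, not a randomised effect of SABR. The direction of the mismatch is not certain either. Section 4.1 allows ECOG 2, whereas 98% of the source trial was ECOG 0-1, and this could lower the reference rate. The documents contain no 6-month PFS for ipilimumab alone in patients with 1-3 sites. All of this stands. It is why the error is shown over a range and why the point is not that 15% has been shown to be too low.

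Three stronger readings are tempting, and the documents do not support them.

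- Section 1.2.3 says of attempted complete resection in oligometastatic melanoma that "they found a median relapse-free survival of 5 months compared with the historical baseline of 1.7 months". Under a constant hazard, 5 months gives 2^(−6/5) = 43.5% at 6 months, and a reader might treat that as the rate without benefit. It is not. The comparator is ipilimumab alone, and section 1.1 makes aggressive local treatment with SABR part of the intended effect, so ablation belongs to what is tested. Relapse-free survival after resection is also a poor proxy for mWHO PFS counted from enrolment.
- Section 1.5.3 reports for previously untreated patients: "The median PFS was 2.8 months in the ipilimumab" arm. The same conversion gives 2^(−6/2.8) = 22.6%. That regimen was 10 mg/kg with dacarbazine. The reported hazard ratio of 0.76 also does not fit exponential curves with medians of 2.8 and 2.6 months, which imply 2.6/2.8 = 0.93. It is not an estimate of the missing rate.
- Section 1.2.1 says of the source trial "71% had M1c stage, 12% had a history of previously treated brain metastasis", and that 38% had elevated LDH. These look like contrasts, but this protocol gives no M-stage mix, sets no LDH limit, and admits lung, liver, brain, adrenal and vertebral disease.

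**Conclusion.** The text is wrong as written on three things: the population the 15% is said to describe, its source (two accounts that disagree), and the 10% type I error claimed for this population. That error holds only if the ipilimumab-alone rate in the analysed patients is no more than about 15.1%, a condition the documents neither state nor support with data.

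If the rate were 18-30%, the rule would call the regimen promising 21% to 79% of the time with no SABR benefit. These figures are exact binomial probabilities conditional on an assumed rate. A rate above 15% is plausible from the way patients are selected, but not proven.

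A reader might go further and infer that 8/32 would be a false positive, or that local treatment without a combination benefit already exceeds the 35% target. Neither follows. The supportable conclusion is that 8/32 cannot separate a SABR effect from patient selection. The point should be fixed, but it does not invalidate the sample-size arithmetic.

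**What to change.** 1. In section 7.1 and the Study Summary, describe 15% as the assumed 6-month PFS for ipilimumab alone in previously treated metastatic melanoma not selected for 1-3 sites. Give one source in both places and remove the reference to maintenance therapy.
2. In section 7.1, state the rule's false-positive probability for reference rates of 15-30%, as in the table above. Limit the conclusion from 8/32 to 6-month PFS exceeding 15%, and say that the excess cannot be attributed to SABR as opposed to patient selection. Note that this conclusion is at the one-sided 10% level: because the tail probability at 15% is 9.6%, above 2.5%, an exact two-sided 95% interval at 8/32 will still include 15%.
3. In section 7.2, specify that the interval is exact and report the observed rate beside the 15-30% range. Show the rate separately for treatment-naive and previously treated patients, descriptively only, since the subgroup sizes are unknown and the total is 32.

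The cost is wording in two places, one small table and two descriptive rows. No patients are added and the cut-off stays at 8. The downside is a narrower claim from a positive result.

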#### **1.5.2 Clinical Safety with Ipilimumab**

##### ***Overview of Clinical Trials Experience***

Because clinical trials are conducted under widely varying conditions, the adverse reaction rates observed cannot be directly compared with rates in other clinical trials or

experience with therapeutics in the same class and may not reflect the rates observed in clinical practice.

The clinical development program excluded patients with active autoimmune disease or those receiving systemic immunosuppression for organ transplantation. Exposure to ipilimumab 3 mg/kg for four doses given by intravenous infusion in previously treated patients with unresectable or metastatic melanoma was assessed in a randomized, double-blind clinical study (MDX010-20). One hundred thirty-one patients (median age 57 years, 60% male) received ipilimumab as a single agent, 380 patients (median age 56 years, 61% male) received ipilimumab with an investigational gp100 peptide vaccine (gp100), and 132 patients (median age 57 years, 54% male) received gp100 peptide vaccine alone. Patients in the study received a median of 4 doses (range 1 to 4 doses). Ipilimumab was discontinued for adverse reactions in 10% of patients.

The most common adverse reactions ( $\geq 5\%$ ) in patients who received ipilimumab at 3 mg/kg were fatigue, diarrhea, pruritus, rash, and colitis.

Table 1 presents selected adverse reactions from MDX010-20, which occurred in at least 5% of patients in the ipilimumab-containing arms and with at least 5% increased

incidence over the control gp100 arm for all-grade events and at least 1% incidence over the control group for Grade 3–5 events.

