### **7.3 Subject Population(s) for Analysis**

All subjects enrolled in the study received at least two doses of ipilimumab and SABR will be used for analysis of the primary endpoint.

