### **7.4 Interim Analysis- Safety**

Prior use of 3mg/kg ipilimumab alone has resulted in a 10-15% grade 3+ autoimmune related toxicity rate. If the addition of SABR to ipilimumab doubles the risk of grade 3+ autoimmune related toxicity, that would be unacceptable. Therefore, our null hypothesis will be that 70% or more of the patients will be severe immune related toxicity-free. We will conduct an interim analysis after the treatment of 18 patients to assess the null hypothesis versus the alternative hypothesis of 90% or more of the patients will be severe immune related toxicity-free. If at the interim analysis 14 or more patients are severe immune related toxicity-free then we will continue to enroll to the planned enrollment of 32 patients. If 5 or more patients have severe immune related toxicities we will consider this combination too toxic for further investigation.

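### The 10% Type II error needs 32 evaluable patients, but total enrollment is also set at 32, with no replacement rule and no boundary for a smaller evaluable number

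*Combined protocol and SAP*

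**What the plan says.** Section 7.1 sets the null at "if at most 15% of patients are progression-free and alive at 6 months" and the target at "an improvement in the 6-month PFS rate to at least 35" percent. It fixes the error rates ("Constraining the Type I and II error rates to 10% each") and states that "the study design will require 32 evaluable patients to test these hypotheses regarding the 6-month PFS rate". Eight or more successes among those 32 is promising; seven or fewer is not sufficiently active.

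Evaluable is a restricted set. Under Section 7.3, enrolled subjects who "received at least two doses of ipilimumab and SABR will be used for analysis of the primary endpoint". Section 7.2 uses patients who received ipilimumab and SABR as the denominator of the 6-month rate, and in its paragraph on overall response defines evaluable in the same terms as Section 7.3.

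Enrollment carries the same number. If the safety interim is passed, Section 7.4 says "then we will continue to enroll to the planned enrollment of 32 patients". The synopsis lists 32 subjects. Section 7.1 derives the study duration from 32 accruals: 16 months at two per month, and "the maximum is 32 months (1 accrual per month for 32 patients").

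Section 6.10 provides for patients who miss SABR because of adverse events after the first two infusions, and Section 4.5.1 lists further grounds for withdrawal. There is no attrition allowance, no replacement rule, and no success boundary for an evaluable number other than 32.

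**The concern.** The number enrolled and the number evaluable can both be 32 only if every enrolled patient receives two doses and SABR. SABR falls at about weeks 5-6, so each patient has several weeks in which to drop out of the primary analysis. The design has almost no slack: 32 is the smallest single-stage sample size that meets 10%/10% for these two rates.

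One count decides whether the regimen is called promising. If enrollment stops at 32 and some patients are not evaluable, a regimen with a true 35% rate is turned down more often than the stated 10%. The plan also does not say how to judge 7 or 8 successes among, say, 29 patients. That choice would be made after the data are seen.

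**Working it through.** **Inputs.** From Section 7.1: p0 = 0.15, p1 = 0.35, Type I and Type II error 0.10 each, 32 evaluable, success at 8 or more. Sidedness is not stated; the rule points one way, so alpha is taken as one-sided. Attrition before SABR is not given and is varied below.

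**Formula.** With n evaluable patients and boundary r, the chance of declaring success is P(X ≥ r | n, p) = 1 − Σ(k = 0 to r−1) C(n,k) p^k (1−p)^(n−k). Alpha uses p = 0.15 and power uses p = 0.35.

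**The plan's own figure.** With n = 32 and r = 8, alpha = 0.0958 and power = 0.9182. The stated 10%/10% is reproduced.

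**A fixed number lost, 32 enrolled, boundary kept at 8.**

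| Evaluable | Alpha | Power | Type II error |
|---|---|---|---|
| 32 | 9.6% | 91.8% | 8.2% |
| 31 | 8.2% | 89.9% | 10.1% |
| 30 | 7.0% | 87.6% | 12.4% |
| 29 | 5.9% | 84.9% | 15.1% |
| 28 | 4.9% | 81.8% | 18.2% |
| 27 | 4.0% | 78.2% | 21.8% |

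**Random attrition.** If each of 32 enrolled patients is lost with probability d, unrelated to outcome, the number of evaluable successes is Binomial(32, 0.35 × (1−d)).

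- d = 5%: p = 0.3325, P(X ≥ 8) = 88.3%, which is 3.5 points below 91.8%.
- d = 10%: p = 0.315, P(X ≥ 8) = 83.7%, which is 8.1 points below.
- The loss first reaches 5 points at about d = 7%.

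**Can a new boundary recover the power?** The table gives the smallest r with alpha at or below 10%.

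| Evaluable | Boundary | Alpha | Power |
|---|---|---|---|
| 26 | 7 | 8.3% | 85.8% |
| 27 | 7 | 9.9% | 88.5% |
| 28-31 | 8 | 4.9-8.2% | 81.8-89.9% |
| 32 | 8 | 9.6% | 91.8% |
| 33 | 9 | 5.0% | 86.8% |
| 34 | 9 | 5.9% | 89.1% |
| 35 | 9 | 6.9% | 91.1% |
| 36 | 9 | 8.0% | 92.7% |

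At 28-31 the boundary stays at 8 and nothing is recovered. At 26-27 it falls to 7. Keeping 8 at 33 evaluable would give alpha 11.1%, above the limit, so 8 cannot be carried upward either.

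**Two-stage design.** The synopsis names a two-stage Simon minimax design. An exact search also finds 32 as the smallest total: stop at 2 or fewer of 17, then reject the regimen at 7 or fewer of 32, with alpha 9.1% and power 90.5%. The final boundary is the same and the starting power is slightly lower.

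**The case against.** **The plan's arithmetic is right.** At 32 evaluable the rule does what Section 7.1 claims. This stands. The fault lies in using one number for two different quantities.

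**The text can be read as accrual until 32 are evaluable.** Section 7.1 and the synopsis both express the requirement in evaluable patients, and on that reading no power is lost. But nothing says that patients are replaced, and Section 7.4 and the duration arithmetic point to 32 enrolled. If replacement was meant, those two figures are too low as soon as anyone is lost.

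**A reader might infer a loss of at least 5 points at ordinary attrition.** The documents do not support that. Such a loss needs about 7% random attrition, or three patients not evaluable. One or two losses cost 1.9 or 4.2 points. The nearest figure is in Section 1.5.2, "Ipilimumab was discontinued for adverse reactions in 10% of patients", but it covers up to four doses in a previously treated population. Here, stopping after the second dose and SABR leaves the patient evaluable. Section 1.5.2 places the usual onset of immune-related events at 3 to 10 weeks, so some come after SABR. Section 3.1.2 recommends completing all four doses despite apparent early progression if performance status is stable, which limits losses from that cause.

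**A reader might also infer that 8 applies whatever evaluable number is reached.** Section 7.1 ties it to the 32 evaluable patients. For other numbers the plan is silent, so the power figures above show what follows if 8 is carried over.

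**Loss may be related to outcome.** If 35% were the rate among all enrolled and every non-evaluable patient were a failure, the count of successes would still be Binomial(32, 0.35) and the chance of 8 or more would stay at 91.8%. Section 7.1 frames the test on evaluable patients, so the calculation follows that framing, but the condition has to be stated.

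**Conclusion.** The point holds as an inconsistency between the enrolled and evaluable numbers. Unless no patient is lost before SABR, either the enrollment figure or the stated 10% Type II error is wrong. With 32 enrolled, one loss takes the Type II error just past 10%, and four losses take it to 18.2%.

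The size within that range rests on three assumptions: an attrition rate that the documents do not give, a 35% rate among evaluable patients with loss unrelated to outcome, and a single-stage test. The documents do not establish any particular loss of power for this trial. Any bias from leaving early losses out of the primary analysis is a separate question, not addressed here.

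**What to change.** In Sections 7.1 and 7.4 and the synopsis, give the enrolled and evaluable numbers separately, then choose one of two routes.

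1. **Keep enrollment at 32.** Restate power over the plausible evaluable range, about 82-90% for 28-31 evaluable, with the assumptions above. Prespecify the boundary for the number reached: 7 or more for 26-27, 8 or more for 28-32. State that this does not recover power at 28-31.
2. **Replace non-evaluable patients until exactly 32 are evaluable.** This keeps alpha at 9.6% and power at 91.8%. Correct the enrollment and duration figures to match. As an illustration under assumed attrition, 32/0.95 = 33.7 gives 34 enrolled (17-34 months at 1-2 per month), and 32/0.90 = 35.6 gives 36 enrolled (18-36 months). If accrual could overshoot, add a boundary of 9 or more for 33-36 evaluable, noting that power at 33 and 34 is 86.8% and 89.1%.

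If the two-stage design in the synopsis is the intended one, the restated power and any boundaries should be computed for it.

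The first route costs a short table and a slightly less favourable stated power, with no extra patients. The second costs a few more patients and a somewhat longer stated accrual.
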